3.D. Clinical, Cognitive, Social, and Adaptive Functioning Assessments and Schedule. Patients referred from [name] current VA Merit study will already have been screened/diagnosed using the Structured Clinical Interview for DSM-5 Disorders (SCID),⁴⁶ Structured Interview for DSM-5 Personality Disorders (SCID-PD),⁴⁷ and the C-SSRS.⁴⁴ We use the SCID-PD given our interest and prior work in borderline personality disorder (BPD), and because many high-risk Veterans meet criteria for BPD, e.g., see³⁰. These three assessments will be reviewed for any interested participants once they have consented for the current study. Additionally, the Ruminative Response Scale⁴³ will be administered during the screening process to determine whether they meet the study inclusion criteria for poor cognitive control problems (see **3.C. Inclusion**). Participants will be enrolled in the intervention and undergo assessments (**Table 3.D**) at the various timepoints: pre- (**Baseline**), post-intervention (**Week 10**) and follow-up (**Week 20**) to be administered in person and abiding by strict COVID-19 safety precautions (e.g., health screening on day prior and day-of visit, temperature check, socially distanced throughout visit, sanitization of all testing materials and furniture before, during, and after each visit).

Following baseline assessments, Veterans will participate in the CR+Bridging sessions (2x/week for 10 weeks; i.e. 20 sessions) via telehealth with a clinical neuropsychologist ([name]/Co-I, who will administer all treatment sessions and train MIRECC Advanced Psychology Fellows on the intervention). [name] (Co-I) will conduct all clinical assessments blind to the patients’ progress in the CR+Bridging sessions.

Table 3.D. Clinical, Cognitive, Social, Adaptive Functioning Assessment Schedule. Primary outcome variables are **bold** font.

Assessment:	Domain	Baseline (Pre-Tx)	Week 10 (Post-Tx)	Week 20 (Follow-Up)
Demographics	Demographics	X		
Structured Clinical Interview for DSM-5 Disorders ⁴⁶	Diagnostic	X		
Structured Clinical Interview for DSM-5 Personality Disorders ⁴⁷	Diagnostic	X		
Columbia-Suicide Severity Rating Scale (C-SSRS) ⁴⁴	Diagnostic	X	X	X
Ruminative Response Scale ⁴³	Rumination	X	X	X
Cognitive Remediation Fidelity Scale ¹⁰	Fidelity		X	
Patient and Therapist Satisfaction Questionnaire (see Appendix 5)	Feasibility/Acceptability		X	X
Intrinsic Motivation Inventory ⁴⁸	Motivation	X	X	
Revised Helping Alliance Questionnaire ⁴⁹	Therapeutic Alliance		X	

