Iowa Gambling Task¹¹⁻¹² (with alternate decks)	Problem-solving	X	X	X
Tower of Hanoi ⁵⁰ (with parallel versions)	Problem-solving	X	X	X
Stroop Test ⁵¹ (with parallel versions)	Cognitive inhibition	X	X	X
Go/No-Go ⁵² (with parallel versions)	Motor inhibition	X	X	X
Naming Test/Neuropsychological Assessment Battery, ¹⁴ Form 1 & 2 (Control test; not expected to change with intervention)	Naming/Control test	X	X	X
Montgomery-Ashberg Depression Rating Scale¹³	Depression	X	X	X
The Personal & Social Performance Scale ²	Social	X	X	X
The Work & Social Adjustment Scale ³	Social, Occupational	X	X	X
Questionnaire for assessing the impact of the COVID-19 pandemic and accompanying mitigation efforts on older adults ¹⁵	Impact of COVID-19	X	X	X
Longitudinal Interval Follow-up Evaluation Range of Impaired Functioning Tool, LIFE-RIFT ¹⁶	Functional impairment	X	X	X

3.E. CR+Bridging Training, Fidelity, Acceptability, and Feasibility. Members of our research team (Drs. [name] and [name]) have extensive experience developing psychosocial interventions in civilian and Veteran samples and establishing their fidelity. CR+Bridging training will include weekly supervision of [name] with [name] or [name] and a modified version of the Cognitive Remediation Fidelity Scale¹⁰ (see **Appendix 6**) will be employed to assess fidelity to the manual. [name] will also oversee implementation of supplementary measures of potential moderators of the intervention (e.g., motivation for treatment and baseline sets of work habits,⁴⁸ quality of therapeutic relationships⁴⁹).

Acceptability will be examined via survey responses (see **Appendix 5**) completed by the patients and therapist at the completion of the intervention and follow-up (Weeks 10 and 20). Feasibility will be measured in

several ways. This includes: (1) ease of implementation—operationalized as less than 60 hours per cycle from start/preparation through intervention delivery until conclusion of follow-up assessment; (2) recruitment, attendance, and retention (operationalized as >75% successful recruitment and 75% attend >15 sessions); and (3) training and fidelity of therapist to CR+Bridging will be conducted at Week 10 (see **Appendix 6**).

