3.F. Timeline. As shown in **Table 3.F**, the CR+Bridging open trial will be conducted with six groups (each group including six Veterans for the 10-week intervention) during months 4-16 with Week 10/Post-tx and Week 20/Follow-up sessions conducted during months 8-21. Data collection will be completed in month 21, followed by data analysis. Manuscript writing and CSR&D Merit Award RCT application submission will occur during months 23-24. A potential limitation that may impact the success of this project is recruitment of Veterans during this challenging time of COVID-19. However, a strength of the proposed clinical intervention study is that it involves telehealth, making it more appealing to participants and less prone to high no-show rates.

Table 3.F. Study Timeline.	Year:	1	1	1	1	1	1	1	1	1	1	1	1	2	2	2	2	2	2	2	
	Month:	1	2	3	4	5	6	7	8	9	10	11	12	13	14	15	16	17	18	19	20
Train staff/Obtain IRB approval:		x	x	x																	
Conduct open trial: Group #				1	1	1	2	2	3	3	3	4	4	5	5	5	5	5	5	5	
Note: Each group includes 6																					
Veterans/patients: 6 groups x 6 = 36 (total)																					
Conduct baseline/pre-tx assessments:			x		x			x		x			x								
Week 10/post-tx & 20/follow-up assessments:								x	x	x	x	x	x	x	x	x	x	x	x	x	
Data entry/analysis:				x	x	x	x	x	x	x	x	x	x	x	x	x	x	x	x	x	
Submit papers and RCT VA Merit Award																		x	x	x	
																		x	x	x	

3.G. Statistical Approach. Rationale for Proposed Sample Size (which applies to all aims): We used data from a similar CR study in civilians⁵³ to determine our sample size. Hamilton Depression Rating Scale (self-report measure that includes the same symptoms as the clinician-administered MADRS¹³ which we will use in the proposed study) scores from pre- and post-CR intervention from Naismith et al⁵³ were used to provide estimates of change in depression severity that we can apply to the MADRS. Using a sample size of 22 achieves 90% power to detect a mean of paired differences of 3.2 with an estimated standard deviation of 4.35 for differences and with a significance level of 0.05 using a two-sided paired t-test. For the current pilot study, we will enroll 36 Veterans in the intervention and we conservatively anticipate up to 40% attrition. This means that even with only 22 completers, we will still be well-powered for the proposed analyses.

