Aim 1: Sample size: Definitive conclusions about the efficacy of the CR+Bridging intervention cannot be made based on this pilot study's findings. We plan to use the data collected to: (1) calculate power for a larger confirmatory study and (2) examine acceptability and feasibility data. We plan to submit a VA Merit application that will involve a rigorous RCT to determine efficacy of this novel intervention.

Analysis: We will calculate descriptive statistics, e.g., means, standard deviations, minimum, maximum for continuous measures (e.g., CR+Bridging treatment fidelity ratings, retention), as well as count and frequencies for categorical measures (e.g., attendance). We will be able to compare these descriptive statistics to published rates of recruitment, engagement, and attendance of similar type interventions.

Aim 2: Sample Size: Using a two-sided paired t-test to compare MADRS¹³ before and after for each subject, for 90% power at a 5% level of significance and assuming a decrease in MADRS with a range of standard deviations from 1 to 10, we can detect a mean paired difference of -0.7 to -6.5 for 22 Veterans.

Analysis: MADRS¹³ and Iowa Gambling Task (IGT^{11, 12}) scores are the primary outcome variables here. For all of the study completers, each outcome measure will be compared initially between Baseline and Week 10 (pre- vs. post-intervention) by paired t-test. As a secondary analysis, all outcome measures in Table 3.D will be compared this way as well. Correction for multiple comparisons will be performed using a Holm's correction.

For exploratory analyses, outcome variables that reach significance for Pre-tx/Baseline vs. Post-tx/Week 10 comparisons will also be analyzed across all three time points (Baseline, Week 10, Week 20/Follow-up) using a linear mixed-effects model with unstructured correlation between time points.

Missing data will be assumed to be missing at random and handled accordingly by multiple imputation. All statistical tests will be 2-tailed with alpha=0.05.

Aim 3: Sample Size: This aim is exploratory. We will utilize the same sample size as shown in the sample size section and acknowledge that we may be underpowered for these analyses.

Analysis: Each outcome measure (e.g., QACPOA¹⁵, LIFE-RIFT¹⁶) will be compared initially between Baseline and Week 10 by a paired t-test and if either show significance, then they will be compared across all three time points using the same mixed-effects model analysis as described in Aim 2.

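### Acceptability is surveyed only at Weeks 10 and 20, with no survey described for Veterans who discontinue, so the result may come mainly from those who stayed and may overstate acceptability.

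*Combined protocol and SAP*

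**What the plan says.** Section 3.E states that acceptability is examined through survey responses "completed by the patients and therapist at the completion of the intervention and follow-up (Weeks 10 and 20"). Table 3.D agrees: the row "Patient and Therapist Satisfaction Questionnaire (see Appendix 5") is marked at Week 10 and Week 20 and nowhere else, and the table has no column for early termination. Sections 1.C and 3.D place the assessments at these time points in person, although the treatment sessions are by telehealth.

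The sample-size rationale in section 3.G says "we will enroll 36 Veterans in the intervention and we conservatively anticipate up to 40% attrition" and concludes that "even with only 22 completers, we will still be well-powered for the proposed analyses".

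Under Aim 1, section 3.G lists two uses for the data: to power a larger study, and to "examine acceptability and feasibility data". The Aim 1 analysis is descriptive. It gives no denominator for acceptability and no rule for survey non-response. Multiple imputation, assuming data missing at random, appears under Aim 2.

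**The concern.** Veterans who leave because the groups, the telehealth format or the exercises did not suit them hold much of the information about acceptability. If the only survey comes at the end of treatment and at follow-up, and nothing describes how someone who has stopped would be reached, the patient result will tend to be drawn from those who stayed. High satisfaction among completers is compatible with poor acceptability among all enrolled. The Aim 1 summaries, as described, would neither reveal nor bound the difference. Acceptability is one of the things this pilot sets out to learn before a randomised trial is proposed.

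**Working it through.** **Inputs.** From section 3.G: 36 enrolled, attrition of up to 40%, 22 completers. From section 3.E and Table 3.D: survey at Weeks 10 and 20. The acceptability rates below are assumptions, because the documents give none.

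**Step 1: the plan's own figures.** The plan says "Using a sample size of 22 achieves 90% power to detect a mean of paired differences of 3.2 with an estimated standard deviation of 4.35", "with a significance level of 0.05 using a two-sided paired t-test". The noncentrality is 3.2/4.35 × √22 = 3.45 on 21 degrees of freedom. Exact power is 0.908, and n = 21 gives 0.894, so 22 is the smallest number reaching 90%. Also 36 × (1 − 0.40) = 21.6, which rounds to 22. The planned figure of 22 is reproduced.

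**Step 2: who may go unheard.** At the ceiling, 36 − 22 = 14 Veterans. The survey would then represent 22/36 = 61.1% of those enrolled, with 14/36 = 38.9% missing if they are not followed up.

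**Step 3: bias of a completers-only rate.** Let *m* be the number not surveyed, *p_c* the rate among those surveyed and *p_d* the rate among those not surveyed. Then

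bias = *p_c* − [(36 − *m*) *p_c* + *m* *p_d*]/36 = (*m*/36) × (*p_c* − *p_d*).

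With *m* = 14 the multiplier is 0.389:

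| Assumed gap, *p_c* − *p_d* (points) | Bias (points) |
|---|---|
| −20 | −7.8 |
| 0 | 0 |
| 10 | 3.9 |
| 20 | 7.8 |
| 30 | 11.7 |
| 50 | 19.4 |

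**Step 4: bounds over all enrolled (illustrative).**

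- 20 of 22 completers satisfied: 20/22 = 90.9% (exact 95% CI 70.8% to 98.9%). Over all 36 the rate lies between 20/36 = 55.6% and (20 + 14)/36 = 94.4%.
- 80% of completers satisfied, 14 not surveyed: (22 × 0.8)/36 = 48.9% to (22 × 0.8 + 14)/36 = 87.8%.
- 80% of completers satisfied, 8 not surveyed: (28 × 0.8)/36 = 62.2% to (28 × 0.8 + 8)/36 = 84.4%.

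The confidence interval in the first case covers sampling error among completers only. It says nothing about the 14 who were not asked.

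**The case against.** Five points can be made on the other side.

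- **Direction.** A reader might infer that the survey does overstate acceptability. The documents do not support that, because they contain no views of Veterans who leave. A zero gap gives no bias and a negative gap gives understatement. Only *may overstate* stands.
- **Exclusion.** A reader might infer that those who stop are barred from the survey. No sentence says so. Weeks 10 and 20 could be calendar visits to which they are still invited, and Appendix 5 and the Human Subjects section are not in the text available. This stands, but other wording leans the other way. Section 3.E ties the first survey to the end of the intervention, Aim 2 analyses study completers, and an in-person visit is a higher barrier than a telehealth session for someone who has left.
- **The ceiling.** The 40% is a conservative allowance made to protect power. The team's earlier cognitive remediation study, in 19 Veterans with schizophrenia, had no dropouts during treatment. Its earlier trial in Veterans at high suicide risk had about 59% completing treatment. So 14 missing is the planned extreme, though within the team's own experience.
- **Dropout is visible.** Retention and attendance are separate feasibility measures. If 14 left having attended 15 sessions or fewer, at most 22/36 = 61% could meet the attendance criterion, against its 75% (27 of 36). That would show how many left, but not whether the intervention was the reason.
- **Consequences.** A reader might infer that the design of the later trial rests on the satisfaction rate. Section 3.G states no satisfaction threshold and no decision rule based on it.

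The imputation under Aim 2 is not an answer. Even if it were extended to the survey, a missing-at-random assumption would not remove bias where leaving depends on unmeasured dissatisfaction.

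**Conclusion.** The point holds as a risk of selection bias in one component of Aim 1, and it is best treated as a cheap improvement. It is not a contradiction or a calculation error, and it does not affect the power calculation. The survey is scheduled only at Weeks 10 and 20, no route to Veterans who discontinue is described, and up to 14 of 36 may be unheard. Upward bias is the plausible direction, since dissatisfaction is an obvious reason to leave, but neither direction nor size can be established from the documents. At the attrition ceiling each 10-point gap between those who stayed and those who left moves the reported rate by 3.9 points. With fewer leaving, the effect shrinks in proportion. These figures assume that everyone who stays responds, that nobody who leaves does, and that the form can be summarised as a proportion satisfied.

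**What to change.** In section 3.E and a footnote to Table 3.D:

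- Offer the existing Appendix 5 patient questionnaire, or its applicable items, by phone or telehealth at discontinuation to Veterans who stop early, and at Week 10 to all others. The Week 20 survey stays as it is.
- If the form does not already ask why a Veteran stopped, add one item that does.

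In the Aim 1 analysis:

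- Report the number responding out of all 36 enrolled and show non-responders separately.
- Give best- and worst-case bounds over the 36 as a sensitivity summary, counting all non-responders first as satisfied and then as not satisfied.

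The cost is a few lines of text and at most about 14 short remote contacts at the attrition ceiling. The reported rate may be less favourable. Because Appendix 5 is not in the text available, the team should check which items suit someone who attended only a few sessions. Reporting over all enrolled and giving the bounds need no new data.

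### The Aim 2 detectable difference of -6.5 at SD 10 does not follow from the stated two-sided 5% test with 22 Veterans: the value is about -7.3, and -6.5 has about 83% power.

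*Combined protocol and SAP*

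**What the plan says.** Section 3.G, Aim 2, Sample Size, sets out the calculation for MADRS, one of the two primary outcomes of this aim (the other is the Iowa Gambling Task). The test is named: "Using a two-sided paired t-test to compare MADRS". The targets are given: "for 90% power at a 5% level of significance". Variability is covered by a range: "with a range of standard deviations from 1 to 10". The result is that "we can detect a mean paired difference of -0.7 to -6.5 for 22 Veterans".

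Two other statements in Section 3.G bear on this figure:

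- The Aim 2 Analysis text fixes the sidedness for the whole plan: "All statistical tests will be 2-tailed with alpha=0.05".
- The Rationale for Proposed Sample Size, which is said to cover every aim, uses the same test, alpha, power and number of completers: "Using a sample size of 22 achieves 90% power to detect a mean of paired differences of 3.2". It takes a standard deviation of 4.35, identified there as that of the paired differences.

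**The concern.** For a paired t-test with sample size, alpha and power all held fixed, the detectable difference is proportional to the standard deviation of the differences. Moving from SD 1 to SD 10 must therefore multiply it by exactly ten. The printed pair, 0.7 and 6.5, fits that only if the common multiple is about 0.65 and the first figure is a rounding of 0.65. The plan's main calculation implies a larger multiple for the same design: 3.2 / 4.35 = 0.736, or about 7.4 at SD 10. The two statements cannot both describe a two-sided 5% test with 90% power and 22 completers.

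What is at stake is the plan's claim about sensitivity when MADRS change is more variable than assumed. The working SD of 4.35 comes from Hamilton scores in a civilian study, not from MADRS in Veterans, so the true value is uncertain. The range of standard deviations is the only place where the plan shows what happens at other values, and its high-variability end is wrong in the favourable direction. The plan also intends to use the pilot data to power a later confirmatory trial. If the figure came from a one-sided set-up, reusing that set-up would carry the error forward.

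**Working it through.** **Inputs, all from Section 3.G**

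- Two-sided paired t-test, alpha 0.05, power 90% (Aim 2, Sample Size; sidedness repeated in Aim 2, Analysis).
- n = 22 completers, so 21 degrees of freedom.
- SD from 1 to 10, read as the SD of the paired differences. The Aim 2 sentence does not say which SD is meant; the Rationale paragraph uses the SD of differences.

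**Formula**

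Let d = difference / SD. The test statistic follows a noncentral t distribution with n - 1 degrees of freedom and noncentrality d × √n. Two-sided power is the probability that it exceeds the 97.5% point of the central t distribution (2.080 for 21 degrees of freedom) plus a negligible lower-tail term. The detectable difference is the d that gives 90% power, multiplied by the SD.

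**Step 1. Reproduce the plan's main calculation**

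- d = 3.2 / 4.35 = 0.736; noncentrality = 0.736 × √22 = 3.45.
- Power is 90.8% at n = 22 and 89.4% at n = 21.

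So 22 is the smallest n that reaches 90%. The Rationale calculation reproduces under the exact two-sided t-test, which confirms the method.

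**Step 2. Apply the same method to the Aim 2 range**

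Solving for 90% power at n = 22, two-sided 0.05, gives d = 0.725 (noncentrality 0.725 × √22 = 3.40).

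| SD of differences | Two-sided detectable difference | Plan states |
|---|---|---|
| 1 | 0.725 × 1 = 0.725 | 0.7 |
| 4.35 | 0.725 × 4.35 = 3.15 | 3.2 (Rationale) |
| 10 | 0.725 × 10 = 7.25 | 6.5 |

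Only the SD 10 entry fails: 6.5 / 7.25 = 0.897, about 10% too small.

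**Step 3. What 6.5 actually delivers at SD 10**

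- Noncentrality = 0.65 × √22 = 3.05, giving two-sided power of 82.8%.
- For 90% power at d = 0.65: n = 26 gives 89.0% and n = 27 gives 90.2%, so 27 completers are needed.
- With 22 completers, 6.5 has 90% power only up to an SD of 6.5 / 0.725 = 8.97.

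**Step 4. Could rounding or another method give 6.5?**

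| Variant (n = 22, SD 10) | Detectable difference |
|---|---|
| Two-sided, 90%, exact t | 7.25 |
| Two-sided, 90%, normal approximation | 6.91 |
| Two-sided, 85%, exact t | 6.70 |
| Two-sided, 80%, exact t | 6.26 |
| One-sided 5%, 90%, normal approximation | 6.24 |
| One-sided 5%, 90%, exact t | 6.45 |

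Rounding does not explain the gap: 6.55 at SD 10 still has only 83.4% two-sided power. Of these variants only the one-sided 5% t-test rounds to 6.5 (one-sided power at 6.5 is 90.4%), and it contradicts the stated test.

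**The case against.** The strongest reply is that nothing in the design depends on this figure. The sample size rests on the Rationale calculation, which reproduces. SD 10 is about 2.3 times the plan's working value (10 / 4.35), and at the working value the detectable difference of 3.15 agrees with the plan's 3.2. The study is a single-arm pilot that disclaims definitive conclusions on efficacy. All of this stands and limits the weight of the point. It does not make the printed figure right.

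A second reply is that the SD might be that of the scores rather than of the differences. A score SD of 10 at both visits gives a difference SD of 10 × √(2(1 - r)), which equals 8.97 when the pre-post correlation r is about 0.60, and 6.5 would then be correct. But the plan states no correlation, and its companion calculation uses the SD of differences. On this reading the SD 1 figure would also become about 0.65.

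A third reply is that the one-sided explanation is conjecture. That is fair. One-sided testing gives 0.645 at SD 1, which rounds directly to 0.6, not 0.7, so it does not match both printed ends cleanly. A two-sided test with 27 completers gives 6.48, and a typing slip is also possible. The origin of the figure is unknown, but the error does not depend on it.

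**Conclusion.** The point holds. Under the stated two-sided 5% paired t-test with 90% power and 22 Veterans, the detectable MADRS difference at SD 10 is 7.25, not 6.5. At 6.5 the power is 82.8%, about 7 points below the stated 90%. The lower end of the range (-0.7 at SD 1) is correct to the precision given.

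The conclusion assumes that the quoted SDs are those of the paired differences, as in the plan's main calculation. The consequence is confined to the claimed sensitivity at high variability. The choice of 22 completers, the enrolment of 36 and the planned analyses do not change.

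**What to change.** In Section 3.G, Aim 2, Sample Size, change the range to -0.7 to -7.3 and say that the SDs are those of the paired differences. If a different SD or a one-sided calculation was intended, the text should say so and be reconciled with the two-tailed rule in the Aim 2 Analysis text. Whoever ran the calculation should check the sidedness setting before it is reused to size the confirmatory trial.

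A separate, optional addition: if Holm's correction is applied across the two primary outcomes, its first step tests at 0.025. The multiple at that level is 0.800 and the range becomes -0.8 to -8.0. The plan does not clearly define that family, and the correction above does not depend on it.

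The cost is one figure and a clarifying phrase. The stated sensitivity becomes slightly less favourable.

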2.A. Suicide Prevention Randomized Clinical Trial (RCT). The PI ([name]) has extensive research experience working with high-risk suicidal individuals (both Veterans and civilians). She has published >20 papers on borderline personality disorder and MDD, including a RCT examining Dialectical Behavior Therapy (DBT) in Veterans at high risk for suicide with her colleague, [name] (Co-I on this study).^{29, 30} The RCT was funded by the Department of Defense and involved DBT (12-months) and 18-month follow-up in suicidal Veterans at the JJPVAMC (PI: [name]). PI [name] also received a supplemental grant (MPIs: [name] & [name]) that involved a rigorous clinical assessment and psychophysiology component. The results indicated that affective startle modulation (non-verbal psychophysiological measures of emotion processing mediated by the amygdala) is exaggerated during unpleasant picture processing in Veterans at high risk for suicide (i.e. multiple attempters) and shows promise as a predictor of a future suicide attempt.³⁰ For the RCT component, we consented 368 Veterans and 324 completed the clinical assessments. Approximately 59% of the sample completed the 6-month DBT trial and 51% were retained at the 12-month follow-up. Over 100 Veterans participated in the supplement study.³⁰ This underscores our ability to recruit and retain a large sample size of Veterans at risk for suicide and conduct a treatment trial in this population. The proposed pilot study will recruit the majority of Veterans from the PI's current VA Merit examining the neurobiology of suicidal behavior using MRI. To date, we have recruited >200 Veterans for this Merit study and of those, ~100 met our stringent criteria and received extensive clinical assessments, neurocognitive assessments, and a MRI scan. We will also recruit outpatients, if necessary. [name] (Co-I), a full-time psychiatrist in the Psychiatry OPD Care Center at the JJPVAMC will facilitate recruitment.

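### The primary Baseline-to-Week 10 test is limited to undefined completers and conflicts with the plan's own missing-data rule; with up to 14 of 36 lost, the estimate can be biased in either direction

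*Combined protocol and SAP*

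**What the plan says.** All of this is in section 3.G unless noted.

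- **Primary outcomes and test (Aim 2, Analysis).** MADRS and IGT "scores are the primary outcome variables here". The comparison is a paired t-test: "For all of the study completers, each outcome measure will be compared initially between Baseline and Week 10".
- **Missing data (end of Aim 2).** "Missing data will be assumed to be missing at random and handled accordingly by multiple imputation". The sentence does not say which analyses it covers, what the imputation model contains, or whether non-completers are imputed.
- **Mixed model (Aim 2, exploratory).** A mixed model with unstructured correlation is planned, but only conditionally: "outcome variables that reach significance for Pre-tx/Baseline vs. Post-tx/Week 10 comparisons will also be analyzed across all three time points".
- **Attrition (sample size rationale).** Of 36 enrolled, "we conservatively anticipate up to 40% attrition", leaving 22 completers. This is the nearest the supplied text comes to a definition.
- **Attendance (section 3.E).** "75% attend >15 sessions" is a feasibility target and is not linked to the analysis set.
- **Use of the data (Aim 1).** The pilot disclaims definitive efficacy conclusions, but its data will be used to "calculate power for a larger confirmatory study".

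**The concern.** Completer can be read in at least three ways: attended enough sessions, had a Week 10 assessment, or finished Week 20. Under the first and third readings, Veterans whose Baseline and Week 10 values were both observed can be left out of the primary test. Under the second, imputation has little left to fill in that test. If non-completers are imputed, the test is no longer completer-only. Two analysts following the text could report different primary results, and the choice could be made after the data are seen.

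The choice also affects bias. MAR lets dropout depend on observed values such as baseline severity. If baseline severity also predicts change, the mean change in those who remain differs from the mean change in all who enrolled. The plan's own assumption therefore does not support its own primary test. The mixed model that could use every Veteran with a baseline value is no safeguard, because it is run only after the completer test has already been significant.

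At stake is the estimate of change from a pilot meant to inform the planning of a randomised trial.

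**Working it through.** **1. The plan's own figures.** Inputs from section 3.G: mean paired difference 3.2, SD of differences 4.35, two-sided alpha 0.05, n = 22. The noncentral t distribution with 21 degrees of freedom gives 90.8% power, so the stated 90% reproduces. For attrition, 36 × (1 − 0.40) = 21.6, rounded to 22 completers. That leaves 36 − 22 = 14 excluded, and 14/36 = 0.389.

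**2. Error of the completer mean.** With dropout fraction f:

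completer mean − all-enrolled mean = f × (completer mean change − dropout mean change)

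Each 1-point difference between the two groups shifts the estimate by 0.39 points at f = 14/36, or by 0.25 at an assumed loss of 9/36. If the groups differ by 3.2 points (assumed), the error at the ceiling is 0.389 × 3.2 = 1.24 points. A completer mean of 3.2 would then correspond to an all-enrolled mean of 1.96 or 4.44, depending on who improved more.

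**3. Dropout that satisfies MAR (simulation).** Change = 3.2 + 4.35(r·z + √(1 − r²)·e), where z is standardised baseline severity and e is independent noise. Retention probability = expit(a + b·z), with a set to give the stated retention. The values of r and b are assumptions, not document figures. Positive b means more severe Veterans stay. Mean improvement in completers, against a true 3.20:

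| Retained | r | b = −1.0 | b = −0.5 | b = 0 | b = +0.5 | b = +1.0 |
|---|---|---|---|---|---|---|
| 22/36 | 0.3 | 2.78 | 2.96 | 3.20 | 3.44 | 3.63 |
| 22/36 | 0.5 | 2.50 | 2.80 | 3.20 | 3.60 | 3.90 |
| 27/36 | 0.3 | 2.93 | 3.05 | 3.20 | 3.36 | 3.48 |
| 27/36 | 0.5 | 2.73 | 2.94 | 3.20 | 3.46 | 3.66 |

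**4. An all-enrolled estimator using baseline.** Take the completer mean plus slope × (all-enrolled baseline mean − completer baseline mean). With two time points and dropout at the second, this is the maximum-likelihood mixed-model contrast. In 20,000 trials of n = 36 per scenario it averaged 3.2 to within about 0.02 throughout.

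- At 22/36 retained, its standard error is about 0.9 to 1.0, against 0.91 to 0.94 for completers. The largest increase is about 8%.
- At 27/36 retained, it is 0.82 to 0.86, against 0.83 to 0.85.
- Root mean squared error at 22/36: with b = −1.0 and r = 0.5, 1.15 for completers against 0.95; with b = +0.5 and r = 0.3, 0.96 against 0.95.

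**5. Effect on the test.** With a true change of zero, r = 0.5, b = ±1.0 and 14 of 36 lost, the completer t-test rejects about 12% of the time, against 4.7% when dropout is completely at random.

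**6. Limit of the remedy.** Let retention depend on the change itself (log-odds ±0.5 to ±1.0 per SD of change, 22/36 retained). The completer mean is then 4.01 to 4.61, or 2.40 to 1.79. The MAR estimator is still off, at 3.81 to 4.50, or 2.59 to 1.90.

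**The case against.** The strongest reply has four parts.

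- **Natural reading.** The sample size paragraph treats completers as the enrolled less attrition, and a paired test needs both values. The natural reading is therefore Veterans with a Week 10 assessment, with imputation left for other gaps such as Week 20. This is plausible, and definitions may exist in the human subjects section or appendices, which are not in the supplied text. But even on this reading the primary test is a complete-case change score that MAR does not justify.
- **Attrition may be lower.** The 40% is called conservative. Section 2.B reports 79% mean attendance and no treatment dropouts in an 8-week group cognitive remediation study at the same centre. With little loss the error is close to zero. That study had 19 Veterans with schizophrenia, however. In the team's trial in Veterans at high risk for suicide (section 2.A), "Approximately 59% of the sample completed the 6-month DBT trial". The analysis has to work at the ceiling the plan sets for itself.
- **The size is assumed and modest.** This stands. Every MAR shift in the table is at most 0.70 points, below one standard error, and at the mild end the gain in root mean squared error is negligible. The simulation uses the MADRS planning figures; nothing comparable is available for IGT, where only the formula in step 2 applies.
- **It is a single-arm pilot.** A pre-post mean is not the between-arm effect on which a randomised trial is powered, and efficacy conclusions are disclaimed. This lowers the weight of the point. It does not remove the reason to fix a cheap inconsistency in advance.

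**Conclusion.** The concern holds and should be fixed. The ambiguity is certain on the supplied text: completer is undefined, and the imputation sentence is not tied to any analysis. The bias is a risk, not an established fact. It is zero if dropout is unrelated to change, and the documents give no outcomes for dropouts, so neither its direction nor its size can be known in advance.

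The per-point shift of 0.39 at the attrition ceiling is arithmetic. The range of 2.50 to 3.90 around 3.2 rests on an assumed baseline-change correlation of 0.3 to 0.5 and retention log-odds of 0.5 to 1.0 per SD of baseline severity. Under those assumptions the all-enrolled estimator removes the bias at little cost in precision. If dropout depends on the change itself, it removes only a small part.

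**What to change.** 1. For MADRS and IGT, make the Week 10 minus Baseline contrast in all enrolled Veterans with a baseline value the primary analysis. Use the mixed model already named, or multiple imputation that includes baseline, and do not make it conditional on a significant completer test.
2. Define completer, and state which analyses the imputation sentence covers.
3. Keep the completer paired t-test as a labelled sensitivity analysis. The existing power statement (22 pairs) describes that test, and the text should say so.
4. Add one delta-adjusted sensitivity analysis for dropout not at random, over a range fixed before the data are seen. The documents give no basis for a particular delta. With 14 of 36 lost, each point of delta applied to the dropouts moves the all-enrolled mean by 0.39.

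The cost is SAP wording and slightly more analysis work, with no extra patients or visits. The downside is that the estimate or its confidence interval may be less favourable, with a standard error up to about 8% larger in the illustration.
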